STUDY PROTOCOL

Title: Exploring Use of a Real-time, Remote Monitoring and Follow-up System for Home-based, HIV Self-testing Among High-risk Men Who Have Sex With Men (MSM)

NCT#: NCT02876926

Date of document: Last reviewed and approved by Brown IRB on 9/15/18

Analysis plan. Monthly survey responses were first aggregated across the entire study period for each of the study's key outcomes: HIV testing rates, STI testing rates, receipt of risk reduction counseling, receiving prevention supplies, PrEP referrals, and being prescribed PrEP. Linear or Poisson regression models with planned contrasts were then used to explore differences in these outcomes between the study groups across the entire 7-month study period. Next, we used survey completion dates to examine rates of each outcome across the 3-month study intervals (baseline, 3-months, and 6-months), which align with current CDC recommendations for HIV testing every 3-6 months among high-risk MSM. Repeat testing was defined as having tested at least twice in at least two of these intervals over the course of the study period. To explore the effect of condition outcomes over time, we used generalized estimating equations (GEE) with binomial distributions and logit-link functions for binary outcomes, and Poisson distributions and with log-link functions for count outcomes. All models were analyzed using an intent-to-treat (ITT) approach that involved retaining participants who withdrew from the study and assuming that they did not engage in any key outcome. Significance was defined as p -values ≤ 0.05 . All analyses were conducted in Stata 14.

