Secondary Aims: We will also explore potential within- and between-subject effects of Enhanced HBST versus standard HBST on positive/negative affect, social support, sex risk behavior, and health empowerment.

Overview of the research: During a “start-up” period of 6 months, we will use qualitative methods (focus group [$N=8$], individual interviews [$N=10$]) to inform ongoing consultation with Devicix (an electrical and software engineering firm) on refining a mobile technology for monitoring HBST use, ultimately preparing it for deployment. Then, during the “study phase,” 40 high-risk MSM in the Providence, RI area will be randomly assigned to one of two conditions: An “enhanced” HBST condition ($N=20$) or standard HBST ($N=20$). In both conditions, 3 HBST kits will be sent by mail at 3-month intervals over the course of 6 months (baseline, 3-months, 6-months). We chose to deliver HBSTs by mail given recent evidence that a majority of MSM prefer this method of receiving kits (as opposed to pharmacy pickup or vending machines)^{50,51}. In the “enhanced” HBST condition, mailed test enclosures will be equipped with a mobile monitoring sensor (see Section 3C.3.1.) that triggers an alarm on dedicated mobile phones carried by qualified HIV test counselors (QHTC). QHTCs will then conduct a follow-up call to the user within 24 hours. In the HBST alone condition, test kits will simply be mailed to participants with contact information for local HIV care, confirmatory testing, STI testing, and PrEP. All participants will be oriented to the study during a baseline, in-person appointment at Brown University. Then, participants will complete monthly assessments online over the course of 7 months while on the study (see Fig. 1 for a timeline). To complete the project within the 2-year period, 4 participants per month will be recruited on a rolling basis (beginning in month 6 of year 1), allowing all participants to finish the study by month 10 in Year 2.

C.2 Participant Population

The research has three phases: (1) Focus group phase [$N = 8$], (2) individual interview phase [$N = 10$], and (3) pilot study phase [$N = 40$]. *All* participants (regardless of which phase they are participating in) will meet the same criteria.

Inclusion criteria are as follows:

1. Biologically male
2. Aged 18 or older

3. Have not been tested for HIV in the last year

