Experimental conditions. In this 7-month longitudinal study, 40 participants will be randomized to receive either “enhanced” HBST ($N=20$) or standard HBST ($N=20$). All will have 3 OraSure® test kits shipped to their homes 1-week after baseline, 3-months, and 6-months. Those in the “enhanced” HBST condition will receive follow-up calls within 24 hours after opening their tests. Those in standard HBST will be provided contact information for local services in their test kits, in addition to the information provided by OraSure®.

Measures. Demographics, past HIV testing history, sexual behavior, and other relevant variables will be collected at baseline. Throughout the 7-month study period, participants will complete online assessments each month inquiring about whether they used a study-provided HBST kits in the last month and what the result was. Items will also assess whether they were provided referral to a local agency for additional prevention services (e.g., additional HIV testing, STI testing, PrEP consultation, HIV risk reduction counseling) by a professional in the last month, and whether they sought each service over the last month. Participants will also complete Timeline Follow Back (TLFB^{55,56}) assessments of their sexual behavior over the past month. The TLFB has proven to be one of the more reliable and valid assessments available for sexual behaviors⁵⁷⁻⁶⁴, and recent evidence suggests that optimal accuracy in reporting may be achieved with short follow-up periods (e.g., 30 days)⁵². Monthly online assessments will also measure general positive/negative affect over that time using the positive and negative affect scales of the PANAS-X⁶⁵, a 20-item scale that asks participants to rate various emotion words according to the extent they have “felt this way over the past month,” on a 1 (*very slightly*) to 5 (*extremely*) scale. These subscales have excellent psychometric properties when used to measure trait affect⁶⁵. Health empowerment will be measured each month using the Patient Activation Measure (PAM-13⁶⁶), and social support will be assessed with 3 subscales of the Received Support Scale (Emotional, Informational, Satisfaction). Both measures have excellent psychometric properties⁶⁶⁻⁶⁹.

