
Figure 3. Timeline of study assessments

perceptions of “enhanced” HBST or HBST alone, additional procedures/services they might have preferred. Those in the “enhanced” condition will be asked about their impressions of counseling over the phone and the usability of the monitoring method. Participants will be paid \$20 for completing the baseline in-person appointment and \$15 per monthly assessment (\$105 total), with a \$55 bonus for completing all assessments on time (within +/- 5 days of being assigned).

Planned Analyses/Power Considerations. As this is a preliminary study, the primary goal is to explore evidence for the feasibility, acceptability, and utility of “active” monitoring and follow-up with HBST, as well as its effects on testing likelihood and frequency compared with usual HBST. As such, data analysis will be primarily descriptive. To address Aim 1, we will explore the number of successful phone contacts with those in the “enhanced” HBST condition, whether contacts involved counseling and/or referral, and qualitative data/ratings of acceptability, feasibility, and preferences. To address Aim 2a, we will compare the overall number of participants reporting any HBST use and the mean number of tests used across the conditions over the study period. To address Aim 2b/c, we will also compare the number of participants receiving HIV test counseling, referral for additional prevention services, and the number who successfully followed-up with these services. Finally, to address the secondary aims, we will compare mean frequencies of unprotected anal sex (condomless or without having taken PrEP that day) and mean levels of positive/negative affect, health empowerment, and social support by condition and testing status. We are aware of the limitations of relying on small scale studies for generating broad conclusions about the efficacy and/or effect sizes of interventions⁹⁶. As such, we are primarily interested in examining the pattern of results, rather than definitively testing hypotheses. We believe a sample size of 40 should allow some exploration of the direction of effects, while remaining within the scope of an exploratory project.

C.5. Human Subjects Involvement, Characteristics, and Design

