Participants will be recruited from the community using ads in popular gay social networking mobile apps (e.g., Grindr, Jackd, Scruff). Participants expressing interest in the study will be screened online. Those meeting eligibility criteria will be contacted by phone and email to schedule an in-person appointment to begin the study. Next, participants will complete baseline measures online. Then, participants will be randomized to a condition. For those in the "enhanced" condition, RAs will inform participants about the study's purpose and guide them in downloading study software onto their smartphones. Although participants will not need to actively provide any input through the app, RAs will instruct participants to keep the app installed, their Bluetooth sensor enabled, and their phones near them throughout the 7-month study. RAs will also ask participants to notify them as soon as possible if they lose their phone or get a new one, their data is erased, or if their service plan changes. Next, RAs will inform all participants that they should expect to receive an email each month with a unique link, and that clicking this link will allow them to complete their monthly assessments. They will also be informed that HBST kits will be mailed to them 1 week after their appointment, and then again in 3 months and 6 months, which they can choose to take or not. However, should they choose to do so, those in the "enhanced" condition will be told that they should expect a call from a QHTC associated with the study within 24 hours after opening their test, and that these calls are intended to provide counseling and referrals after taking the test (which participants can refuse). Finally, participants will be asked to complete a 30-minute follow-up interview about the study via phone after completing the study. They will be informed that they can pick up payments for completing study assessments at the research offices anytime during or after the study.

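### The SAP names no baseline covariate for its HIV-testing models, although testing history is collected before randomisation; one pre-named covariate would probably gain precision at almost no cost

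*SAP*

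**What the plan says.** - **What is collected.** Protocol C.4, Phase II, Measures: "Demographics, past HIV testing history, sexual behavior, and other relevant variables will be collected at baseline".
- **When.** Protocol C.5 gives the order: "Next, participants will complete baseline measures online. Then, participants will be randomized to a condition". Testing history is therefore a true pre-randomisation variable.
- **Who enters.** The entry rule in Protocol C.2 is "Have not been tested for HIV in the last year". It admits both men who have never tested and men whose last test was more than a year ago.
- **Allocation.** Protocol C.1 (Overview of the research) and C.4 give 20 men per arm. Neither describes stratification or blocking.
- **Models.** SAP, Analysis plan: "Linear or Poisson regression models with planned contrasts were then used to explore differences in these outcomes between the study groups", followed by GEE models for condition over time. No baseline covariate is named for any model, and the SAP does not state that the models are unadjusted.
- **How results will be read.** Protocol C.4, Planned Analyses/Power Considerations: "We believe a sample size of 40 should allow some exploration of the direction of effects". The SAP adds a threshold: "Significance was defined as p -values ≤ 0.05".

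**The concern.** Aim 2a concerns any and repeat HIV testing. Among the listed baseline items, past testing history is plausibly the one most closely related to that outcome. As written, neither the allocation nor the analysis uses it.

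With 20 men per arm, a noticeable difference in the number of never-testers is not unusual. If never-testers use fewer kits, the arm that receives more of them will look worse for a reason unrelated to the intervention. Adjustment would remove that part of the difference and, where history is prognostic, narrow the interval.

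If adjustment was intended but not written down, the choice of covariates stays open until after the data are seen.

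**Working it through.** The sample size of 40 carries no effect size, SD or power, so there is no plan figure to reproduce.

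**Inputs from the documents.** 40 men, 20 per arm; at most 3 kits per man; threshold 0.05 (two-sided assumed).

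**Inputs assumed, because the documents do not give them.**
- Never-testers: 20% to 50% of the 40, that is K = 8 to 20 men.
- Per-kit use in never-testers v past testers: 40% v 65% (25-point gap) to 30% v 75% (45-point gap).
- Intervention effect: +10 points per kit, or 3 × 0.10 = 0.30 tests.
- Some within-man correlation across kits (beta-binomial counts).

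**Step 1: how often the arms differ.** With K never-testers among 40 split 20/20, the number X in one arm is hypergeometric: P(X = x) = C(K, x) · C(40 − K, 20 − x) / C(40, 20). The between-arm difference is |2x − K|, which has the same parity as K.
- K = 8: a difference of 4 or more means x ≤ 2 or x ≥ 6, probability 23.5%.
- K = 9: the difference is odd, so it must be at least 5 (x ≤ 2 or x ≥ 7), probability 13%.
- K = 20: x ≤ 8 or x ≥ 12, probability 34.3%.

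Over K = 8 to 20 the range is about 13% to 34%. Treating the arms as independent binomial samples instead gives 16%, 23% and 27% at shares of 20%, 30% and 50%.

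**Step 2: what an imbalance does.** Four men in 20 is 20 points. Shift in mean tests = imbalance × 3 kits × gap:
- 0.20 × 3 × 0.25 = 0.15
- 0.20 × 3 × 0.45 = 0.27

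Against the assumed effect of 0.30 tests, that is 50% to 90% of the effect.

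**Step 3: precision.** In simulated 20 v 20 trials, a linear model on arm alone was compared with arm plus never-tested.
- Mild case: the standard error falls from 0.328 to 0.316, and 1 − 0.316/0.328 = 4%. The equivalent gain in men is (0.328/0.316)² − 1 = 8%.
- Strong case: it falls from 0.353 to 0.292, and 1 − 0.292/0.353 = 17%. The equivalent is (0.353/0.292)² − 1 = 46%.
- Other within-man correlations move this only modestly: 4% to 18% at a correlation of 0.3, and 3% to 14% at 0.5. About 3% to 17% is a fair summary.
- If history is not prognostic, the standard error rises by 1% to 2%.

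**Step 4: error rates.** A separate simulation used about 12,000 trials per scenario, per-kit use of 70% in control past testers, and gaps of 0, 20 and 40 points.
- No true effect, all randomisations: false-positive rate 4.6% to 5.2%, with or without adjustment.
- No true effect, given a difference of 4 or more men: 9.4% to 9.9% unadjusted v 4.5% to 5.1% adjusted (40-point gap); 6.1% to 6.6% v 4.5% to 4.8% (20-point gap).
- True effect of +20 points per kit: overall power rises with adjustment from 35–42% to 44–49% (40-point gap) or from 42–47% to 44–49% (20-point gap). It falls by about 1 point if the gap is zero.

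**The case against.** The strongest reply is that nothing here is invalid. Randomisation protects the unadjusted comparison, and Step 4 confirms an overall false-positive rate near 5%. The protocol also says "we are primarily interested in examining the pattern of results, rather than definitively testing hypotheses", so no powered hypothesis is harmed. Both points stand and limit the weight of the criticism. They do not remove it: the direction of effects is what the protocol hopes to learn, an imbalance shifts exactly that, and the SAP applies a significance threshold.

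Second, the size depends on a never-tester share and a prognostic gap that the documents do not give. The entry rule already removes recent testers, which narrows the contrast. The SAP counts withdrawn men as having no outcome, which would dilute any link between history and testing; Step 3 includes no withdrawals. This also stands, which is why the result is given as a range that includes the case where adjustment slightly hurts.

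Third, the SAP is silent on covariates; it does not state that the models are unadjusted. That is true, but silence leaves the choice open.

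Fourth, the SAP is written in the past tense, so pre-specification may no longer be possible. The fix allows for this.

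**Conclusion.** The point holds as a matter of precision and of conditional distortion. A baseline variable plausibly related to the Aim 2a outcomes is available before randomisation, and neither the described allocation nor any named model uses it. On the stated assumptions, an imbalance of 4 or more never-testers occurs in about 13% to 34% of randomisations, a 20-point imbalance shifts mean tests by 0.15 to 0.27, and adjustment cuts the standard error by about 3% to 17%. If history is not prognostic, it costs 1% to 2%.

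Three stronger readings are not supported:
- A reader might infer that omitting the covariate creates spurious effects in general. It does not: the inflated false-positive rate appears only given an imbalance that has occurred.
- A reader might infer that adjustment clearly lowers the chance of an estimate in the wrong direction. Counted strictly, without treating exact ties as wrong, that chance is 17% to 20% unadjusted and 15% to 20% adjusted, with no gain in the mild case.
- A reader might extend the point to the STI and PrEP outcomes. The documents do not specify matching baseline items for these, so it is confined here to HIV testing and repeat testing.

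**What to change.** - State in the SAP whether the models are adjusted.
- Include one covariate, ever tested for HIV before enrolment (never v more than 1 year ago), in the whole-period and GEE models of HIV testing and repeat testing.
- For binary outcomes, report a standardised (marginal) risk difference, because the odds ratio from a logit model changes meaning when a covariate is added.
- Show the unadjusted estimate and its interval alongside, and tabulate testing history by arm.
- If the analysis has already been run, label the adjusted estimate a sensitivity analysis.

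The cost is a short addition to the SAP and one degree of freedom. No new data are needed.

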keep their phone near them as much as possible over the 7-month study. They will also be instructed to inform study staff as soon as possible should they lose their phones, change phones, or their current service contract lapses. One week after the initial appointment, an HBST kit will be sent to participants’ verified addresses. Shipment tracking will be used to record data about when HBST participants receive their tests. In “enhanced” HBST, participants, opening their mailed test enclosure will trigger an alert on the study database, which is monitored regularly by staff QHTCs. These alerts will instruct QHTCs to conduct a follow-up call with participants. QHTCs will be CAAS postdoctoral trainees with Ph.D.’s in clinical psychology who have completed additional training in HIV testing counseling (offered by [name]), suicide prevention intervention (offered by nearby Lifespan Hospital), and study-specific follow-up procedures. QHTCs will take turns placing follow-up calls. QHTCs will conduct calls while in private offices on Brown University’s campus. As such, they will be able to access the study database while conducting the calls, so as to allow check-ins about previous referrals and data entry during calls. QHTCs will follow up with participants within 24 hours after the test is opened. During follow-up calls, QHTCs will verify whether the participant has completed the test, what the result was, and ask whether the participant would like to receive counseling, entering this data into the study database. For reactive results, QHTCs will facilitate appointments for confirmatory testing. For non-reactive results, QHTCs will inquire about participants’ interest in other prevention services (e.g., STI testing, counseling). QHTCs will also screen for suicidality and record this information using the data entry forms, providing intervention/referral if needed. If participants indicate they have not taken the test yet but plan to do so, QHTCs will ask when they plan to take the test and whether there is a better time to contact them again. If a participant cannot be reached during the 24-hour post-test window, the 3 additional follow-up attempts will be made over the following 72 hours. This process will repeat for tests sent at 3 and 6 months. To facilitate monthly study assessments, participants will receive an email with a link to an each assessment specific to that participant and time period. Participants will be asked to complete these on a desktop computer within 2 days of receipt, and failing to do so within that time will prompt the RA to follow up via phone and email to encourage adherence. Once the study is complete, the RA will follow-up with participants over the phone to conduct a 30-minute qualitative interview. This interview will assess participants’

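### Three 3-month intervals do not fit a 7-month study with seven surveys, so by-interval rates and interval effects can show a change when behaviour is constant

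*SAP*

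**What the plan says.** The SAP (Analysis plan) first pools the monthly survey answers over the whole 7 months and compares the arms. It then works by interval: "we used survey completion dates to examine rates of each outcome across the 3-month study intervals (baseline, 3-months, and 6-months". GEE models explore outcomes over time, with a logit link for binary outcomes and a log link for counts. Repeat testing is defined on the same intervals. Participants who withdraw are counted as having no outcome, and significance is p ≤ 0.05. The SAP does not say where one interval ends and the next begins, where the seventh survey belongs, whether an exposure term is used, or whether GEE time is the interval or the monthly survey.

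The protocol sets the schedule:

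- C.1, Overview of the research: "3 HBST kits will be sent by mail at 3-month intervals over the course of 6 months (baseline, 3-months, 6-months", and "participants will complete monthly assessments online over the course of 7 months while on the study".
- C.4, Experimental conditions: "test kits shipped to their homes 1-week after baseline, 3-months, and 6-months".
- C.4, Measures: "participants will complete online assessments each month inquiring about whether they used a study-provided HBST kits in the last month".
- C.4, Procedure: a bonus is paid for "completing all assessments on time (within +/- 5 days of being assigned".

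**The concern.** Three intervals of three months need nine months of follow-up, and the study has seven. Only about one month follows the third kit. If rates of each outcome are set side by side across intervals of different length, an outcome that builds up with time will be lower in a short interval and higher in a long one, whatever participants do.

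At stake is the reading of change over time. A fall in STI testing or PrEP contacts after month 6 could be taken as fading engagement, or a rise in the middle interval as uptake, when both come from the calendar. The rule that withdrawals count as no outcome lowers later intervals further, which would deepen a false decline.

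**Working it through.** **1. Length of follow-up, from the plan's own figures.** The protocol pays $15 per monthly assessment, $105 in total: 105 / 15 = 7 surveys. Recruiting 40 at 4 per month takes 10 months. Starting in month 6, the last enrolment is month 6 + 10 − 1 = 15, and 15 + 7 = 22, which is month 10 of year 2, as C.1 states. Seven months is therefore firm.

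**2. Do the intervals fit?** 3 × 3 = 9 months against 7. Seven surveys do not divide by three, so any cut that uses all of them is unequal. At a constant monthly rate, expected counts are proportional to survey-months:

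| Cut | Surveys | Survey-months | Count ratio, 2nd v 1st | Count ratio, 3rd v 1st |
|---|---|---|---|---|
| Kit dates, by month covered | 1–3, 4–6, 7 | 3/3/1 | 1.00 | 0.33 |
| Completion date, surveys done on or after the due date | 1–2, 3–5, 6–7 | 2/3/2 | 1.50 | 1.00 |
| Equal thirds of 7 months | 1–2, 3–4, 5–7 | 2/2/3 | 1.00 | 1.50 |
| Nearest label (cuts at 1.5 and 4.5 months) | 1, 2–4, 5–7 | 1/3/3 | 3.00 | 3.00 |

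These ratios do not depend on the rate. Their direction depends on a cut that the SAP does not state.

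**3. Binary outcomes.** The documents give no outcome rates. Assume a 3-month risk p of 20% / 50%. Risk over w months = 1 − (1 − p)^(w/3).

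- One month: 1 − 0.8^(1/3) = 0.072; 1 − 0.5^(1/3) = 0.206. Under 3/3/1 the third-versus-first OR is 0.31 / 0.26.
- Two months: 1 − 0.8^(2/3) = 0.138; 1 − 0.5^(2/3) = 0.370. Under 2/3/2 the second-versus-first OR is 1.56 / 1.70, and third-versus-first is 1.00.

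**4. False significance if GEE time is the interval.** Settings: 600 simulated trials each, N = 40, no arm or time effect, exchangeable correlation, with and without between-person heterogeneity (gamma frailty, variance 1), p ≤ 0.05.

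| Model and contrast | p = 20% | p = 50% |
|---|---|---|
| 3/3/1, binary, 3rd v 1st | 31% | 71–80% |
| 3/3/1, Poisson, 3rd v 1st | 35–40% | 86–89% |
| 3/3/1, Poisson with log(months) offset | 8–9% | 5% |
| 2/3/2, binary, 3rd v 1st | 3–5% | 4–6% |
| 2/3/2, binary, 2nd v 1st | 8–12% | 18–22% |

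A second simulation used a joint two-degree-of-freedom test of interval at constant monthly probabilities of 0.10, 0.20 and 0.30 (300 trials each). For Poisson models it gave 46%, 94% and 100% under 3/3/1, 13%, 36% and 46% under 2/3/2, and 4–7% with the offset.

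**5. Arm contrasts.** Both arms share the same windows. For counts at constant rates the window length cancels: (λ₁w)/(λ₀w) = λ₁/λ₀. In the second simulation the Poisson condition-by-interval test rejected in 4–8% of trials, except 13% in the sparsest 3/3/1 setting. For binary outcomes, 50% v 20% over three months is an OR of 4.00; it becomes 3.66 over two months and 3.37 over one.

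**6. Study-kit use.** One kit is sent per interval, so use does not simply accrue with time. Assumptions: month of 30.4 days, 3 days' mail, exponential time to use with median 14 / 30 days, all kits eventually used, 3/3/1 cut. With shipments at about days 7, 91 and 182, the third-to-first count ratio is 0.77 / 0.64. A log(months) offset multiplies this by 3, a false rise of about 2.3 / 1.9. If the one-week lag applies to every kit (about days 7, 98 and 189), the ratio is 0.66 / 0.54 and becomes 1.98 / 1.63 with the offset. Follow-up after delivery of kit 3 is 212.8 − 185.4 = 27.4 days on the first reading and 212.8 − 192.4 = 20.4 days on the second.

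**7. Repeat testing.** Under the assumptions of step 6 with shipments at days 7, 91 and 182, and surveys completed 0–5 days after they fall due, a literal completion-date cut costs about 1% / 7% of on-time users of kits 1 and 2 their repeat-tester status (2% / 9% if 70% of kits are ever used). Assigning surveys to the month covered brings this under 1%.

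**The case against.** The strongest reply is that no stated aim uses the distorted quantity. Aim 2 and the protocol's planned analyses compare arms, the protocol calls its analysis mainly descriptive, and nowhere is the third-versus-first term named as a test of interest. This largely stands and sets the severity. It does not remove the point: the SAP itself compares interval rates for each outcome and explores effects over time, and a study that looks for patterns is exposed to a pattern made by window length.

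The interval label may also mean only the spacing of kits. That is plausible, but the windows are unequal on that reading too. If the first interval were a period before enrolment, three equal windows could exist with month 7 left over. The SAP does not say so, and eligibility requires no HIV test in the past year, so HIV testing in such a window would be zero by design.

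The significance rates depend on the cut, the GEE time unit and assumed risks. This stands; they are conditional figures.

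A reader might infer that the trial's arm comparison is biased. The documents do not support that: the 7-month comparison does not use the intervals, and step 5 shows little movement elsewhere. A reader might also infer that every by-interval count needs an exposure offset. For kit use that would create a false rise, because kits are supplied once per interval.

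**Conclusion.** The point holds for secondary, by-interval results, at low to moderate severity. The mismatch between three 3-month intervals and seven months, and the count ratios in step 2, follow from the documents alone. The odds ratios and significance rates rest on assumed constant risks, and the latter also on the GEE using these intervals. The 31–89% in step 4 is therefore not the trial's overall false-positive rate; under 2/3/2 the artefact is a smaller second-interval rise.

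The outcomes at risk are STI testing, counselling, supplies, and PrEP referral and prescription. The 7-month arm comparison and arm count ratios at constant rates are unaffected; binary arm contrasts and repeat testing are affected slightly. One limit applies to counselling and referrals: in the enhanced arm they are also offered on calls triggered by opening a kit ("QHTCs will follow up with participants within 24 hours after the test is opened"), so a constant monthly rate fits them less well.

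**What to change.** - State the cut-points by the month each survey covers: surveys 1–3, 4–6 and 7. Describe the third interval as about one month. State the GEE time unit.
- For outcomes not tied to kits, report per-month rates. Where they are modelled as counts by interval, add an offset of log(3), log(3) and log(1). Using scheduled months leaves the rule for withdrawals as it is. Where they are binary, fit the GEE to the monthly survey responses, whose windows are equal.
- For study-kit use, apply no offset and report tests per kit. Note that follow-up after the third kit is only about 20 to 27 days, depending on how the shipment dates in Protocol C.4 and C.5 are read, and reconcile those passages. The protocol says "Shipment tracking will be used to record data about when HBST participants receive their tests", so the actual time can be reported.
- Show clinic tests separately in by-interval summaries, but keep them in the HIV-testing and repeat-testing definitions.
- Do not interpret a change between intervals of unequal length, in either direction, as behaviour change.

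The cost is some SAP wording and light re-coding of existing data, with no new survey item. The SAP describes the analysis in the past tense, so results changed in this way should be labelled as added afterwards. The offset is exact only if the monthly rate is constant.

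### Placing outcomes in 3-month intervals by survey completion date can put month-3 and month-6 reports in the wrong interval, because each survey looks back one month

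*SAP*

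**What the plan says.** The SAP (Analysis plan) first aggregates each outcome over the whole study. It then turns to intervals: "we used survey completion dates to examine rates of each outcome across the 3-month study intervals (baseline, 3-months, and 6-months". Repeat testing is built on those intervals: "Repeat testing was defined as having tested at least twice in at least two of these intervals over the course of the study period". GEE models are used to explore condition effects over time. The SAP does not say on which day each interval starts and ends, or how a survey that falls on a boundary is handled.

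The protocol (C.1, Overview) says "participants will complete monthly assessments online over the course of 7 months while on the study". Its Measures paragraph (C.4, Phase II) has the surveys "inquiring about whether they used a study-provided HBST kits in the last month and what the result was", and for other services asks "whether they sought each service over the last month". The described items record whether something happened in the month, not on which date. The Procedure paragraph asks for completion within 2 days of receiving an emailed link to an "assessment specific to that participant and time period". The bonus is for "completing all assessments on time (within +/- 5 days of being assigned" days, as the payment text puts it.

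**The concern.** A completion date marks the end of the reporting window, not the event. The surveys closing months 3 and 6 fall due at about the points where 3-month intervals would naturally be cut. If such a survey is answered just after the cut and placed by its completion date, events from the month just ended are credited to the interval just begun.

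Repeat testing needs tests in two different intervals, so its classification can change in either direction. It is part of Aim 2a. With 20 men per arm, one reclassified man moves that arm's rate by 1/20 = 5 percentage points.

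**Working it through.** The plan gives no figure to reproduce. The checks ask when the completion-date rule fails and by how much.

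**Inputs from the documents.** Seven monthly surveys (payment schedule: $105 / $15 = 7); a one-month look-back; kits sent 1 week after baseline and at about 3 and 6 months; an on-time window of plus or minus 5 days.

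**Assumptions.** 30-day months, surveys due on day 30k, and repeat testing read as at least one test in each of at least two intervals.

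**1. One boundary survey, cut at day 90.** A survey completed on day c, after the cut, covers days c − 30 to c. The share of that window before the cut is (90 − (c − 30))/30 = (120 − c)/30.

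| Completed on day | Placed in interval | Share of window in interval 1 |
|---|---|---|
| 85 or 90 | 1 | 100% |
| 91 | 2 | 29/30 = 96.7% |
| 92 | 2 | 28/30 = 93.3% |
| 95 | 2 | 25/30 = 83.3% |

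The month-6 survey behaves the same way at day 180. With a cut at day 97, every month-3 survey completed by day 95 goes to interval 1, where its window lies.

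**2. Which testing patterns change.** Grouping by month covered gives surveys 1–3, 4–6 and 7. If both boundary surveys are answered after the cut, completion date gives 1–2, 3–5 and 6–7. Of the 21 possible pairs of testing months, 15 count as repeat testing under the first grouping and 16 under the second. They disagree on 7:
- lost: months 3+4, 3+5 and 6+7;
- gained: months 1+3, 2+3, 4+6 and 5+6.

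The gained pairs 1+3 and 2+3 need a test from outside the study, since only one kit has been sent by then. The pairs 4+6 and 5+6 can arise from a late-used first kit plus the second. A man testing in months 1, 4 and 7, soon after each kit arrives, is classified alike under both groupings.

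**3. Size, by simulation.** Additional assumptions: 70% of kits used; kits mailed on days 7, 90 and 180 plus 3 days in the post; tests after day 210 unobserved; surveys answered 0 to 5 days after the due date; cuts at days 90 and 180; 400,000 simulated men per setting.

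| Delay from delivery to use | Tests misplaced | True repeat testing | Repeat testing by completion date | True repeat testers missed |
|---|---|---|---|---|
| Uniform over 90 days | 28.9% | 53.5% | 45.5% | 17.8% |
| Exponential, mean 45 days | 13.5% | 54.0% | 49.9% | 9.6% |
| Exponential, mean 30 days | 8.6% | 63.4% | 59.9% | 6.0% |
| Exponential, mean 15 days | 1.8% | 73.5% | 72.6% | 1.2% |

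A fresh run agreed with these to within about 0.3 points. In the uniform case the net shift is 53.5 − 45.5 = 8.0 points, or 0.080 × 20 = 1.6 men per arm. At mean delay 15 days it is 0.9 points, or 0.009 × 20 = 0.18 men.

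**4. Variants under uniform use.**
- Completion spread over plus or minus 5 days: about 16% of tests misplaced and 12% of true repeat testers missed.
- Shipments on days 7, 97 and 187 with cuts at days 97 and 187: 3.8% missed if the look-back ends on the completion day, and 5.9% if it is the fixed calendar month.

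**The case against.** The strongest reply is that the SAP is incomplete rather than wrong. It says completion dates were used to examine rates across intervals, which is compatible with counting back one month from the completion date. The survey timetable is given mainly in figures missing from the text reviewed. The on-time window allows for early completion, and a survey answered by the cut is placed correctly. The interval labels match the kit times, and one reading of the protocol ships each kit a week after its time point; cuts placed there remove most of the effect.

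All of this stands as a limit on size. It also rules out two stronger readings. A reader might infer that everything in the month-3 and month-6 surveys is misplaced and that repeat testing is therefore misclassified. That needs cuts at exactly 3 and 6 months, placement purely by completion day, and every boundary survey answered late; the documents establish none of these together.

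A reader might also infer bias between arms. If enhanced-arm men used kits with mean delay 30 days and standard-arm men uniformly, the table would give an apparent difference of 59.9 − 45.5 = 14.4 points against a true 63.4 − 53.5 = 9.9. But no document gives kit-use timing by arm, so that contrast is invented. The 4.5-point gap is 0.045 × 20 = 0.9 of a man, against a standard error of about 16 points: √(0.599 × 0.401/20 + 0.455 × 0.545/20) = 0.156.

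The protocol's own Aim 2a comparison (any use and mean number of tests over the study) uses no intervals, and it calls the analysis primarily descriptive.

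What the reply does not remove is that the only placement rule stated is the completion date, and neither document mentions a correction for the look-back. Grouping surveys 1–3, 4–6 and 7 would be sound, but that is placement by survey number, which the SAP does not state.

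**Conclusion.** The point holds as a risk of misplacement at the boundaries, with a better method available from data already held. Under the stated assumptions with cuts at days 90 and 180, between about 1% and 18% of true repeat testers are missed. The upper end needs slow, uniform kit use and every survey answered after its due date; prompt kit users are barely affected. Some false repeat testers are also created. The exposure is confined to interval-based repeat testing and the over-time GEE models. Neither a definite misclassification nor its direction by arm can be read from the documents.

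**What to change.** In the SAP:

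1. State the interval cut-points in days from baseline. Placing them at the ends of survey months 3 and 6 makes them coincide with the months the surveys cover.
2. For surveys answered on time, assign answers by survey number: 1–3, 4–6 and 7. The links are already specific to participant and period, so the number should be on file.
3. For late surveys, assign by completion date minus the one-month look-back.
4. Report repeat testing under the completion-date rule as a sensitivity check, with the number of men whose status changes.

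The cost is a few sentences and a line or so of code, plus a rerun of the interval analyses if they are already done. No new data are needed. A residual error remains: a late survey whose look-back straddles a cut can still be misplaced. If men count back from the day they answer, an on-time survey answered 5 days after its due date also carries 5/30 = 17% of its window from the next month, against 83% on the wrong side under the completion-date rule.
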